2.4 Blinding and Randomization

Subjects will be allocated to treatment groups via the EDC system. Eligible subjects will be randomized stratified by study site 1:1:1:1 in the Run-in Phase and stratified by study site, age group and baseline *B.b. s.l.* serostatus 2:2:1 in the Main Study Phase according to a randomization list created by a statistician. The study will be an observer-blinded trial, which will be conducted in a blinded manner for the study investigators, the sponsor including laboratory personnel, and the subjects. Only designated study staff who randomize subjects into treatment groups and perform preparation and application of the vaccinations will be unblinded. These unblinded study staff members will not be involved with trial conduct otherwise. An overview of persons who will be unblinded is provided below:

Unblinded:

- Designated study site staff who randomize subjects to treatment groups and are concerned with IMP handling (i.e. perform preparation and application of the study vaccine, maintain drug dispensing log detailing the dates and quantities of IMP administered to each subject). These unblinded study staff members will not be involved with trial conduct otherwise.
- CRAs responsible for monitoring of IMP handling and related data for verifying drug accountability during the study and performing overall drug accountability.
- Statistical team at the CRO performing statistical analyses for generation of safety data tables for the DSMB.
- DSMB members.

Blinded:

- Study participants
- Investigators and other study staff involved in general study conduct and safety assessments.
- All other CRAs (responsible for monitoring study data apart from IMP handling/drug accountability).
- All other sponsor and CRO staff including laboratory personnel at the sponsor's labs for immunogenicity assessments.

General unblinding of sponsor staff and ADMB will be done for the IA Day 85 after confirmation that all subjects performed Visit 6 or, in case of missing V6 visits, after the close of the time window for Visit 6. Interim analyses results will be distributed to selected sponsor representatives.

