2.6 Center and Country Effect and Stratification Variables

The center and region effect will be taken into account and estimated by adding study site and region, respectively in ANOVA models. Also other covariates will be used as described in Section 5.3.

Furthermore, selected tables will be presented per study site/region and by other stratification factors. A separate column in the List of Tables (Section 7) defines which tables will be stratified by study site, region (Europe vs. United States), *B.b. s.l.* serostatus at Visit 0, and by age group as marked in Section 7.

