5.1 Data Points

5.1.1 Tables and Listings

[figure not shown]
The following ELISA information will be analyzed and corresponding details on subject level will be provided in data listings:

Summary tables for categorical immunogenicity variables:

- Immunogenicity blood sample availability by time point
- Immunogenicity results/serostatus (report concentration/negative) by OspA serotype by time point (including baseline serology status)
- Subjects by OspA IgG serostatus at baseline
- SCRs for OspA serotype specific IgG by visit
 - each OspA serotype (separate tables for ST1 to ST6)
 - all six OspA serotypes combined
 - ST1 and ST2 combined
- Subjects Reaching an at least 4-fold or a 10- Fold Increase from Day 1 (Visit 1) in OspA-specific IgG Titer by visit
 - each OspA serotype (separate tables for ST1 to ST6)

Summary tables for continuous immunogenicity variables will be provided:

- GMTs for IgG against each OspA serotype (ST1 to ST6) by visit (separate table for each OspA serotype).

- GMFRs as compared to Visit 1 (Day 1) for IgG against each OspA serotype by visit (separate tables for each OspA serotype)

Correlation Analysis:

- Correlation Analyses for each OspA Specific IgG titer with each other OspA Specific IgG titer, respectively, at Day 85 (15 comparisons in total)

Inferential analysis will be performed as described in Section 5.3. Details are specified in Section 7.

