5.3 Inferential analysis

- In general, all statistical tests comparing treatment groups in the immunogenicity analysis will only include the two dose groups chosen for the main phase (i.e. VLA15 135 μ g and 180 μ g groups) and the placebo group. However, summary measures for 90 μ g group will be included in the tables.
- ANOVAs with factors treatment group and study sites will be performed for the comparison between the VLA15 135 μ g, 180 μ g and Placebo group for each OspA ST1 to ST6 respectively. The primary immunogenicity analysis will be the ANOVA for ELISA GMTs at Day 85 in the PP Population.
- ANOVAs will be performed for GMTs as well as GMFRs at all available time points.
- This will be done using log10 transformed data and taking the anti-log of the resulting point estimates for the least squares means, least squares means differences and the corresponding 95% CIs. Tukey's HSD test will be applied for pair-wise comparisons.
- Sensitivity analyses for GMTs and GMFRs will be performed for ANOVAs with factors study site, treatment group, study site*treatment group, age, and B.b. s.I serostatus at baseline.
- Summary tables for the OspA- specific IgG titer against each OspA serotype and summary tables for the geometric mean fold-rise against each OspA serotype will be amended by an overall test (Kruskal-Wallis).
- SCRs will be compared using Fisher-Freeman-Halton tests, a significant overall test will be amended by pair-wise tests (Fisher's exact test). The same will be done for rates of subjects reaching a 4- or 10- fold Increase from Day 1 (Visit 1) in titer.
- A non-parametric correlation analysis (Spearman) between OspA IgG antibodies GMTs for each combination of two different OspA specific IgG types will be performed for Day 85 and VLA15 treatment group separately as well as for all VLA15 treatment groups together (pooled analysis).

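### The primary Day 85 ANOVA leaves out two of the three Main-phase stratification factors, and the only models that include them also add site-by-treatment

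*SAP*

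**What the plan says.** Section 2.4 has the Main phase randomised "stratified by study site, age group and baseline" B.b. s.l. serostatus, 2:2:1. The Run-in was stratified by site alone. Section 2.12 pools the two phases for analysis.

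Section 5.3 sets the primary model: "ANOVAs with factors treatment group and study sites will be performed for the comparison" of 135 µg, 180 µg and placebo, for each of ST1 to ST6, and "The primary immunogenicity analysis will be the ANOVA for ELISA GMTs at Day 85 in the PP Population". Results are back-transformed from log10 as "least squares means, least squares means differences and the corresponding 95% CIs", and Tukey's "HSD test will be applied for pair-wise comparisons". Tables 14.1.3.1.30–35 list the same two factors for GMT, and Tables 14.1.3.1.42–47 do so for GMFR.

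Age and serostatus appear in one place in Section 5.3: "Sensitivity analyses for GMTs and GMFRs will be performed for ANOVAs with factors study site, treatment group, study site*treatment group, age", together with baseline serostatus. Tables 14.1.3.1.36–41 (GMT) and 14.1.3.1.48–53 (GMFR) implement this at Day 85 only, with all five terms each time. Section 2.6 adds no further model; it says "Also other covariates will be used as described in Section 5.3". Section 5.1.1 says "Details are specified in Section 7", and Section 7 gives the covariate as age group where Section 5.3 says age.

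**The concern.** When randomisation is balanced on a factor that predicts titer, a model without that factor leaves its variance in the error term. The estimate stays unbiased, but the standard error is larger than it needs to be, so tests and intervals are somewhat conservative. The primary objective is to choose a dose, so precision on 135 versus 180 µg is what matters most.

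The sensitivity analysis does not fill the gap, because it changes two things at once: it adds the covariates and it adds site-by-treatment. With that interaction in the model, default least-squares means weight every site equally, so unequal site sizes widen the interval. The widening can offset or exceed what the covariates gain. If the two results differ, the reader cannot tell which change caused it. That problem of interpretation does not depend on how strongly age group or serostatus predicts titer.

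**Working it through.** **Inputs from the SAP.** Section 1.4: GMT 61.3 versus 86.1, log10 SD 0.51, 189 per dose group (210 × 0.90), two-sided 5%. Section 1.2: Main phase 180/180/90, age groups about 2:1, about 10% or more seropositive. Pooled arms are 210, 210 and 120, total 540, of which 450 come from the Main phase. Placebo in the PP analysis: 120 × 0.90 = 108.

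**Assumed, because the SAP does not give it.** R², the share of log10-titer variance explained by age group and serostatus together: 0–10%. Site sizes: see step 4.

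**1. The plan's own figure.** d = log10(86.1/61.3) = 0.1475. SE = 0.51 × √(2/189) = 0.0525. Power = Φ(0.1475/0.0525 − 1.96) = 80.3%, which agrees with the stated 80%.

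**2. Effect of adding the two factors.** SE becomes 0.51 × √(1 − R²) × √(2/189). The Tukey critical value for three groups with 189 + 189 + 108 − 3 = 483 degrees of freedom is q/√2 = 2.351. Tukey power is from the noncentral t.

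| R² | SE factor | Power, Tukey | Power, unadjusted 5% | Tukey CI half-width (GMT ratio) |
|---|---|---|---|---|
| 0 | 1.000 | 67.8% | 80.3% | 1.328-fold |
| 1% | 0.995 | 68.3% | 80.7% | 1.327-fold |
| 5% | 0.975 | 70.3% | 82.3% | 1.319-fold |
| 10% | 0.949 | 73.0% | 84.2% | 1.309-fold |

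The drop from 80.3% to 67.8% in the first row comes from Tukey's test and is a separate matter. The covariate effect is the change down each column.

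To see what these R² values require, let each factor shift titer f-fold, with a share 60/210 aged 50–65 and 0.10 seropositive: (log10 f)² × (0.204 + 0.090) = R² × 0.51². This gives f = 1.24, 1.62 and 1.98 for R² of 1%, 5% and 10%.

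**3. How conservative the planned model is.** With perfect balance on the omitted factors, actual alpha at a nominal unadjusted 5% is 2 × (1 − Φ(1.96/√(1 − R²))) = 4.9%, 4.4% and 3.9% at R² of 1%, 5% and 10%. A simulation of the pooled design (Run-in stratified by site only, Main phase in blocks of 5 within strata, 10% PP loss; 5, 10 or 16 sites assumed) gave 4.5–4.6% at R² 5% and 4.1–4.3% at 10%. In the same simulation, Tukey power without versus with the covariates was 67.5–68.0% versus 69.9–70.2% (R² 5%) and 67.8–68.3% versus 72.6–72.9% (R² 10%).

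**4. What site-by-treatment does.** With nᵢ subjects per dose at site i and K sites, the additive model has variance proportional to 2/Σnᵢ. Equal site weighting has (1/K²)Σ(2/nᵢ). The SE ratio is √(mean(nᵢ) × mean(1/nᵢ)). If half the sites are r times larger than the rest:

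| r | SE ratio | × 0.975 (R² 5%) | × 0.949 (R² 10%) |
|---|---|---|---|
| 1 | 1.00 | 0.97 | 0.95 |
| 2 | √(1.5 × 0.75) = 1.06 | 1.03 | 1.01 |
| 3 | √(2 × 0.667) = 1.15 | 1.13 | 1.10 |
| 5 | √(3 × 0.6) = 1.34 | 1.31 | 1.27 |

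A two-fold spread in site size is already enough to hide the gain from a 10% R².

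**The case against.** The strongest reply is that nothing here is wrong. The SAP never promises that every stratification factor enters the primary model, the dose comparison is valid as planned, and the benefit rests on an R² that the documents do not supply. At R² = 0 the gain is nil; at 5% the Tukey half-width goes only from 1.328- to 1.319-fold; and 10% needs each factor to shift titer about two-fold. Age group and serostatus are also examined in stratified GMT tables and in Figures 14.1.3.61–62. Adding one additive sensitivity model would cure the interpretation problem without touching the primary analysis, which may have been fixed in a protocol not seen here.

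Much of this stands as a limit on size. The precision gain is modest and may be zero. With equal site sizes the sensitivity model would show it in full, so the accurate statement is that the model may not show the gain. The alpha figures are at unadjusted 5%, not under Tukey. But the stratified tables and figures are summaries, not adjusted dose contrasts, and they do not replace the missing model. The sponsor considered both factors important enough to stratify on and to model in sensitivity analyses, and the SAP gives no reason for leaving them out of the primary. An extra additive sensitivity model is an acceptable minimum, but it would leave any available precision out of the primary result.

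**Conclusion.** The point holds. The primary GMT model and its GMFR counterpart adjust for one of three Main-phase stratification factors, and no listed model has all three as main effects without the interaction. The consequence is possible loss of precision and an uninterpretable primary/sensitivity contrast; there is no bias or alpha inflation for 135 versus 180 µg. Under Tukey's test the gain in power is 0 to 5.2 percentage points (67.8% to 73.0%) for an assumed R² of 0–10%. Whether the current sensitivity model would show any of it depends on site sizes and on least-squares-mean weighting, neither of which the SAP states. This is a change that should be made, not a flaw that invalidates the analysis. The mismatch between age and age group is one of wording only.

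**What to change.** Before unblinding for IA Day 85:

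- In Section 5.3 and Tables 14.1.3.1.30–35, make the primary model log10 titer = treatment + site + age group + baseline B.b. s.l. serostatus. Specify the Visit 0 serostatus used for stratification, not the Visit 1 OspA IgG status of Section 5.2.
- Use the same additive terms for GMFR (Tables 14.1.3.1.42–47).
- Keep treatment + site as a sensitivity analysis.
- Report site-by-treatment as a separate heterogeneity check, not as the source of the dose-effect estimate.
- Change age to age group in Section 5.3, and record the model change in Section 2.14 if the protocol fixed a different one.

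The cost is SAP wording and reprogramming of Tables 30–35 (with their mITT repeats) and 42–47, including draft outputs that Section 8 says the sponsor has already reviewed. No new data are needed, since both variables are already collected and already used as model terms.

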1. OVERVIEW

1.1 Study Objectives

1.1.1 Primary Objective

- To determine the optimal dose of VLA15 in healthy adults aged 18 - 65 years up to Day 85.

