1.2 Study Design

This is a randomized, observer-blind (subject, sponsor and investigator/ site staff involved in clinical evaluation of subjects are blinded), placebo controlled, multicenter Phase 2 study (see Figure 1).

In the Run-in phase, a total of 120 subjects aged 18 to 40 years were to be randomized stratified by study site 1:1:1:1 to receive VLA15 90 µg w/ alum, VLA15 135 µg w/ alum, VLA15 180 µg w/ alum, or placebo (30 subjects per treatment group) as intramuscular (I.M.) vaccinations on Days 1, 29 and 57. Dosing was to be adjusted by injection volume (see Table 1).

Table 1: Treatment Groups and Vaccinations

Group	Treatment	Injection Volume [mL]	Days of Vaccination
90 µg	VLA15 90 µg w/ alum	0.50	1, 29, 57
135 µg	VLA15 135 µg w/ alum	0.75	1, 29, 57
180 µg	VLA15 180 µg w/ alum	1.00	1, 29, 57
Placebo	PBS	1.00	1, 29, 57

Two safety visits were to be performed after the first vaccination: a safety phone call at Day 4 (i.e. Visit 1a, three days after the first vaccination) and an in-person visit at Day 8 (i.e. Visit 1b, seven days after the first vaccination). After all subjects enrolled in the Run-in phase completed Visit 4 (Day 85, i.e. 28 days after the third vaccination) a Data Safety Monitoring Board (DSMB) reviewed all available safety data up to Day 85 in a scheduled DSMB meeting and gave the recommendation that all treatment groups were safe and well tolerated so far and could be continued in the Main Study phase based on available safety data. After the DSMB meeting, the two higher dose groups (135 µg and 180 µg of VLA15 w/ alum) were selected for further investigation. No safety concerns associated with any of the VLA15 treatment groups were identified by the independent DSMB.

In the Main Study phase, a total of 450 subjects aged 18 to 65 years will be randomized stratified by study site, age group and baseline *B.b. s.l.* serostatus 2:2:1 to receive 135 µg or 180 µg VLA15 w/ alum (180 subjects each) or placebo (90 subjects), as I.M. vaccinations on Days 1, 29 and 57. Subjects will be enrolled in two age groups (18-49 years and 50-65 years) in a ratio of approximately 2:1.

In both study phases, target is to enroll approximately 10 % or more of subjects that are baseline seropositive for *Borrelia burgdorferi sensu latu* (*Bb s.l.*). This is aimed to be achieved through selection of endemic recruitment areas as well as database searches for *Bb s.l.* seropositive subjects.

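### For Day 85 GMTs the SAP plans no direct 135-versus-180 µg estimate within age group, serostatus or region, and the only test on the stratified tables includes placebo

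*SAP*

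**What the plan says.** The primary objective (SAP 1.1.1) is "To determine the optimal dose of VLA15 in healthy adults aged 18 - 65 years up to Day 85". On enrolment in the Main Study phase, Section 1.2 states: "Subjects will be enrolled in two age groups (18-49 years and 50-65 years) in a ratio of approximately 2:1". Randomization in that phase is stratified by site, age group and baseline serostatus, with a target of about 10% or more seropositive subjects. Section 1.3.2 lists GMTs by age group as a secondary endpoint.

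Section 5.3 fixes the analysis:

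- Primary analysis: "The primary immunogenicity analysis will be the ANOVA for ELISA GMTs at Day 85 in the PP Population". For its factors, "ANOVAs with factors treatment group and study sites will be performed", with Tukey pair-wise comparisons. Tables 14.1.3.1.30-35 are marked only for an mITT repeat.
- Sensitivity analysis: "ANOVAs with factors study site, treatment group, study site*treatment group, age, and B.b. s.I serostatus at baseline". Age and serostatus enter as main effects only.
- Summary tables for titres and fold rises: these "will be amended by an overall test (Kruskal-Wallis"). No pair-wise step is given. Tests are limited to 135 µg, 180 µg and placebo.

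Section 7.1.3 marks Tables 14.1.3.1.4-9 for stratification by age group, region and serostatus. Under Sections 2.5 and 2.12 they show N, geometric mean, its CI and the SD of the log values, one column per arm. Figures 14.1.3.61-62 plot Day 85 GMTs by the same factors, one chart per dose.

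On region, Section 2.6 says: "The center and region effect will be taken into account and estimated by adding study site and region, respectively in ANOVA models".

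**The concern.** The trial exists to choose a dose for adults aged 18 to 65, and it deliberately enrols an older group and previously exposed subjects. A natural question is whether the dose preferred overall is also preferred there. The pooled comparison answers mainly for younger adults: with the 30 Run-in subjects aged 18-40 added, about 150 of 210 per dose are aged 18-49.

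For Day 85 titres, none of the planned outputs is a direct dose-against-dose estimate in a stratum. The sensitivity model assumes one dose effect across age and serostatus. The one p-value on the stratified tables is an overall test that includes placebo, so a small value there may reflect only vaccine against placebo, although it stands in a table used to inform dose choice.

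The region point is a plain mismatch: Section 2.6 announces a region term, while neither Section 5.3 nor Tables 14.1.3.1.30-53 contain one.

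**Working it through.** **Inputs from the SAP.** Log10 SD 0.51, GMTs 61.3 and 86.1, 10% PP exclusion, 189 per group for 80% power at two-sided 5% (1.4). Main phase 180/180/90, age ratio about 2:1, Run-in 30 per arm aged 18-40, seropositives about 10% (1.2). Values below 40 U/mL are set to 20 U/mL (5.2).

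**The SAP's own figure.** log10(86.1/61.3) = 0.1475. A two-sample t-test with SD 0.51 needs 188.5, so 189 per group, and has 80.1% power at 189. The stated figure reproduces.

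**PP subjects per stratum.**
- 18-49: (120 + 30) × 0.9 = 135 per dose; placebo (60 + 30) × 0.9 = 81.
- 50-65: 60 × 0.9 = 54 per dose; placebo 30 × 0.9 = 27.
- Seropositive at exactly 10%: 21 × 0.9 ≈ 19 per dose; placebo 12 × 0.9 ≈ 11.

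**What the overall test responds to.** 4,000 simulated three-arm trials per scenario, dose titres log-normal with SD 0.51, and the 40/20 rule applied to all arms. The SAP gives no placebo titres, so two settings are assumed: all placebo values below 40 U/mL, or a noisier placebo with GMT 25 and log10 SD 0.3. Cells show Kruskal-Wallis rejection, all-below-limit placebo / noisier placebo.

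| Stratum | Doses equal (61.3, 61.3) | Doses differ (61.3, 86.1) |
|---|---|---|
| 18-49 | 100% / 100% | 100% / 100% |
| 50-65 | 100% / 99% | 100% / 100% |
| Seropositive | 99.95% / 70% | 100% / 86% |

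With equal doses, a direct 135-versus-180 t-test on log10 titres rejects in about 5% in every stratum, as it should. In both age groups the overall test gives practically the same answer whether or not the doses differ.

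**Precision of the missing quantity.** The 95% CI factor for the 180/135 ratio is 10^(t × 0.51 × √(2/n)).
- n = 135: 1.33. At equal observed GMTs the interval is 0.75 to 1.33.
- n = 54: 1.57, so 0.64 to 1.57.
- n = 19: 2.17, so 0.46 to 2.17.
- One region, if half of subjects (assumed; n = 94): 1.40, so 0.71 to 1.40.

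Power for the SAP's 1.405-fold difference is 66%, 32%, 14% and 51% respectively. The smallest ratio of ratios detectable with 80% power is 10^((1.96 + 0.84) × 0.51 × √(2/n₁ + 2/n₂)): about 2.1 for age (135, 54) and 3.1 for serostatus (170, 19).

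**Why placebo should stay out of the model.** If placebo values are nearly constant, the pooled SD at ages 50-65 falls to about 0.51 × √(108/135) = 0.456, and the CI factor to about 1.49. That interval would be too narrow, and it would slip just under the 1.5-fold mark only because of the placebo arm.

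**The case against.** The strongest reply is that the stratified tables already hold the information. With N, geometric mean and log SD printed for each dose, the unadjusted 180/135 ratio and its interval follow by arithmetic in every stratum. This stands. A reader might infer that the planned output cannot say anything about dose by subgroup, or that it says less than the age-stratified seroconversion tables, which get pair-wise Fisher tests after a significant overall test. The SAP supports neither: a GMT with CI and log SD per dose tells more than a Fisher p-value, and the GMT tables are split by three factors against one for seroconversion.

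It is also fair that the objectives state no subgroup-specific dose question, that the age-group endpoint is descriptive and is delivered, and that interactions are badly underpowered. This limits the remedy to estimation.

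The placebo floor is an assumption, and the seropositive result depends on it heavily. The titre inputs are from Phase 1, and Section 2.14 says the ELISA was later optimised. Section 5.3 does not say outright that the Kruskal-Wallis test is repeated in each stratum. That is the natural reading of a test attached to tables marked as stratified; if it is wrong, the strata have no GMT test at all, and a direct dose estimate is still absent.

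Finally, a region main effect, which is all that Section 2.6 promises, would not compare doses within a region. The mismatch is therefore a separate, smaller item.

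**Conclusion.** The point holds in a limited form. For Day 85 GMTs the SAP prints no 180/135 estimate by age group, serostatus or region; an informal, unadjusted comparison is possible from the tables. The test attached to those tables says little about dose: with equal doses it rejects in 99-100% of trials at ages 50-65 and in roughly 70-100% in seropositives. Those rates assume placebo values mostly below the quantitation limit, Phase 1 titres and SD in every stratum, 10% PP loss in every stratum and exactly 10% seropositives.

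A reader might expect the added estimates to settle the dose question in each subgroup. They would not: at ages 50-65 and in seropositives the interval at equal GMTs does not exclude a 1.5-fold difference, the SAP's own yardstick.

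The contradiction on region between Section 2.6 and Sections 5.3 and 7 rests on no assumption. The primary pooled analysis is untouched by either item.

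**What to change.** 1. In Section 5.3, for each serotype at Day 85, report the 180/135 GMT ratio with 95% CI by age group, by serostatus and by region. Use log10 models fitted to the two dose arms only (or with arm-specific variances) with a treatment-by-subgroup term. In the region model, put region in place of site. Label the results as exploratory estimation and state the expected CI factors: about 1.33 (18-49), 1.57 (50-65) and 2.2 (seropositive, if 10% are enrolled).
2. In the stratified versions of Tables 14.1.3.1.4-9, replace the three-group Kruskal-Wallis p-value with the 135-versus-180 comparison.
3. Reconcile Section 2.6 with Sections 5.3 and 7 on region. In the same edit, align Section 2.14, which brings all dose groups into the comparison, with Section 5.3, which leaves 90 µg out of the tests. Placebo is included under either, so the point above does not depend on it.

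The cost is SAP wording and some extra tables (six serotypes by three factors) from data already collected, with no added subjects or samples. The downside is more exploratory output with wide intervals, widest in seropositives.
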